### 4.2 Randomization

Subjects will be randomized to receive either IV arginine or placebo. Permuted-blocks, stratified by clinical center and age group (<12 vs.  $\geq 12$ ), will be used. Equal allocation randomization tables will be provided by the Data Coordinating Center to the site research pharmacies. Randomization numbers will be delivered to the clinical center staff using a web-based system. This system will use each enrolled patient’s age group (<12 vs.  $\geq 12$ ) to deliver the next assigned treatment. Each site research pharmacy will use a randomization number to look up the treatment assignment and prepare the appropriate study drug. The randomization number will be recorded in the database.

### 4.3 Study Drug Administration

#### 4.3.1 Preparation, Storage & Labeling and Accountability

Study drug will be prepared and blinded from clinical staff and patients by each site research pharmacist. All sites will be responsible for documentation of drug accountability including storage and dispensing information.

#### 4.3.2 Dosing Schedule

Patients age 3–21 years will be randomized to one of two study arms:

- A one-time L-arginine loading dose (200 mg/kg IV) + standard dose (100 mg/kg IV TID); OR
- Placebo (normal saline) loading dose (2ml/kg IV) + 1ml/kg IV TID.

The maximum loading dose will be 20 gm, with a standard dose maximum of 10 gm IV TID, which will continue until ED or hospital discharge, or for 21 doses, whichever comes first. (Dosing can be ordered every 8 hours, but there is TID flexibility)

#### 4.3.3 Discontinuation of Study Drug

Study drug will be stopped if a patient meets any one of the following criteria:

- 1) Neurological dysfunction or development of stroke while on protocol
- 2) Allergic reaction to study medication
- 3) Patient's request
- 4) Abnormal lab results:
  - Hepatic dysfunction: SGPT (ALT)  $>6X$  upper value; OR
  - Renal dysfunction: Creatinine  $>1.2$ ; OR
  - Acidosis with bicarbonate  $<16$

Arginine/placebo will be terminated, but clinical data and research blood collection will continue.

NOTE: This is different than withdrawal from the study. The clinical or research teams may stop study drug administration for development of AEs or SAEs as described above without withdrawing from the study. The participant may also decide to stop study drug without withdrawing consent to participate. See section [4.6 on page 32](#) (Withdrawal from Study) for additional information

#### 4.3.4 Maintaining Blinding during the Study

In the event of adverse events thought to be related to arginine (see above) providers should assume that the subject is receiving active drug (arginine) and take appropriate steps. The clinical team and investigators should not attempt to unblind themselves.

### 4.4 Sample Collection and Processing

Blood (for plasma, erythrocytes and platelets) will be drawn, processed and stored for future batched analyses at the time of presentation prior to study drug delivery (pre-Dose), on day 1 and prior to discharge (or ED discharge, whichever comes first) ([Table 2 on the following page](#)). The impact of IV arginine therapy on global arginine bioavailability will be determined and compared to the placebo arm. Mitochondrial respiratory complex activities will be measured as an indicator of mitochondrial function in platelets; aconitase activity will be measured as an index of mitochondrial oxidative damage. These samples will also serve to establish a SCD-VOE biorepository to explore future mechanistic studies.

Urine or serum pregnancy test results will be reviewed prior to randomization for female participants 13 years or older.

Sample collection, processing, storage, and shipping instructions will be detailed in a separate document.

Table 2: Laboratory monitoring will be undertaken according to the schedule below

	Pre-Dose 	Day 2 	Day 8 or Discharge 
CBC with retic count (clinical)*	X	X	X
Comprehensive metabolic panel	X**	X	
BHCG (girls $\geq$ 13 yrs)	X		
Research Labs (Aim 3)	X	X	X

**1** – Pre-dose is before the start of study drug.

**2** – Day 2 is the day after study drug is administered (starting at midnight of the day the study drug is started)

**3** – Day 8 is the day that the last dose #21 will be given for patients who have not yet been discharged

\*when available clinically

\*\*Last CMP in medical record will be reviewed prior to randomization (up to 12 months): if abnormal (meeting criteria for discontinuation of study drug) or not available, a CMP will be obtained Pre-Dose and reviewed before randomization. Patients with CMP obtained at pre-dose that meet criteria for discontinuation of study drug will be excluded from participation. All other patients will have a CMP obtained on day 2. Patients with ALT  $>$  3X upper limit, creatinine  $>$  1.0 or bicarb of 16 pre-dose or day 2 will have CMP repeated in 24 hours.

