- c – Research labs: will be obtained with routine daily blood draws whenever possible and may be drawn on days when the research and clinical team suspect the patient may be discharged to avoid multiple venipunctures. In the event the patient is not discharged on that date, discharge labs should be drawn again prior to discharge. Baseline labs to be drawn before the start of study drug.
- d – Screening CMP from a clinically ordered CMP or the last CMP in the medical record within the last 12 months will be reviewed. If there are any values within higher than protocol defined cut offs for study drug withdrawal, then a CMP is to be drawn and reviewed prior to randomization. For participants with normal past CMP, a CMP will be done on day 2.
- e – Pregnancy test obtained at Pre-Dose for females 13 years and older.
- f – The first set of Vital Signs (including oxygen saturation) and Pain scores will be captured when the patient first presents to the Emergency Department. The highest and lowest pain scores will be recorded from Day 1 through Day 8 (or within 6 hours of Discharge). The first set of vitals signs after 6 am will be collected up until Day 8/Discharge, whichever comes first. Ensure oxygen saturation is captured at Pre-Dose and within 6 hours of Discharge.
- g – Symptoms Questionnaire will be completed daily through Day 14 or Discharge.
- h – Use of Parenteral Opioids will be documented every shift by nursing staff per standard protocol, including opioids delivered by the PCA device as well as any intravenous, intranasal and/or oral opioids used. Data on daily opioid use will be collected and recorded.
- i – AEs and SAEs will be monitored daily through discharge or through 14 days of hospitalization; Return ED visits and hospitalizations will be followed for 28 days after hospital discharge.
- j – Patients will be randomized within 12 hours of their initial dose of parenteral opioid in the ED or ward and Arginine will be administered TID.

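### Laboratory stop rules run as long as study drug is given (up to dose 21, Day 8), but the last required metabolic panel is on Day 2, or Day 3 if flagged, and the bicarbonate repeat trigger is the single value 16

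*Combined protocol and SAP*

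**What the plan says.** **Dosing.** Section 4.3.2 gives a 200 mg/kg load and then 100 mg/kg three times a day, "which will continue until ED or hospital discharge, or for 21 doses, whichever comes first". Table 2, note 3 adds: "Day 8 is the day that the last dose #21 will be given for patients who have not yet been discharged".

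**Stop rules.** Section 4.3.3 stops study drug for ALT above 6 times the upper value, for creatinine above 1.2, or for "Acidosis with bicarbonate" below 16. No time limit is attached.

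**Scheduled chemistry.** A comprehensive metabolic panel (CMP) up to 12 months old may serve for screening. A pre-dose panel is needed only if that one is abnormal or missing, and a child whose pre-dose panel meets a stop rule is excluded. After that, "All other patients will have a CMP obtained on day 2". Table 3, note d agrees: "For participants with normal past CMP, a CMP will be done on day 2". The CMP row is blank under Day 8 or Discharge in Table 2, and under Days 3–7 and Day 8 or Discharge in Table 3.

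**Repeats.** The Table 2 footnote triggers a repeat for ALT above 3 times the upper limit, creatinine above 1.0, "or bicarb of 16 pre-dose or day 2 will have CMP repeated in 24 hours". Nothing is said about a second repeat.

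**Other monitoring.** Table 3, note i: "AEs and SAEs will be monitored daily through discharge or through 14 days of hospitalization". Note g: "Symptoms Questionnaire will be completed daily through Day 14 or Discharge".

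**The concern.** A laboratory stop rule can act only when there is a laboratory value. Here the rule lasts as long as dosing, but the required testing ends on Day 2, or on Day 3 for a child flagged on Day 2. A child whose Day 3 repeat is still in the watch range needs no further test under the plan.

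The trigger for bicarbonate is also much tighter than for the other two analytes. Acidosis is the risk that Section 2.6 names for the hydrochloride salt. Section 7.4 links overdose to acidosis and hyperkalemia, particularly in renal failure. Table 5 lists renal failure, metabolic acidosis and hyperkalemia among the expected events of the disease. Renal function or acid–base status could therefore change during an admission while drug continues, and a Day 2 panel cannot show a Day 5 change.

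At stake is whether the plan's own stopping limits can operate for children with longer stays. Sample size, power and alpha are not affected.

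**Working it through.** **1. Inputs.** Load 200 mg/kg, then 100 mg/kg per dose, at most 21 doses (Section 4.3.2). Day 2 starts at the midnight after the first dose (Table 2, note 2). Assumptions: dosing every 8 hours (the protocol also allows flexible TID timing), a start at any clock time on Day 1, and the load counted as dose 1. The 20 g and 10 g caps keep the 2:1 ratio, so shares of the total do not change.

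**2. The plan's own figure, dose 21 on Day 8.** Dose 21 falls 20 × 8 = 160 hours after the load. That is Day 8 for starts at or after 08:00 and Day 7 for earlier starts. If the load is followed by 21 standard doses, the last falls at 168 hours, always Day 8. The stated day is reproduced.

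**3. Full course.** 200 + 20 × 100 = 2,200 mg/kg. The first 24 hours hold 200 + 100 + 100 = 400 mg/kg; the rate is then 300 mg/kg per day.

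**4. Dose after the last required panel, full course.**

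| Reference point | Doses given before | Doses after | mg/kg after | Share of 2,200 |
|---|---|---|---|---|
| Day 2 panel, any time that day | 1–6 | 15–20 | 1,500–2,000 | 68–91% |
| End of Day 2 | 4–6 | 15–17 | 1,500–1,700 | 68–77% |
| Day 3 repeat, any time that day | 4–9 | 12–17 | 1,200–1,700 | 55–77% |
| End of Day 3 | 7–9 | 12–14 | 1,200–1,400 | 55–64% |

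The upper ends of the rows for a panel at any time are corner cases: a start just before midnight and a panel just after.

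**5. Shorter stays, dose after the end of Day 2.**

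- Discharge at end of Day 3: 300 of 800–1,000 mg/kg (30–38%).
- Discharge at end of Day 4: 600 of 1,100–1,300 mg/kg (46–55%).
- Discharge at end of Day 5: 900 of 1,400–1,600 mg/kg (56–64%).
- Discharge by end of Day 2: nothing after the end of Day 2.

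**6. Repeat trigger against stop limit.**

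| Analyte | Repeat | Stop | Range that is repeated but not stopped |
|---|---|---|---|
| ALT | >3× | >6× | above 3× up to 6× |
| Creatinine | >1.0 | >1.2 | above 1.0 up to 1.2 |
| Bicarbonate | 16 | <16 | the value 16 |

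With whole-number reporting, a bicarbonate of 17 on Day 2 needs no repeat and 15 stops the drug. Reading the trigger as 16 or lower does not widen the range, because anything lower already stops the drug.

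**7. Effect of added panels.** Take panels on Days 2, 4 and 6 at one clock time. Between panels there are 48/8 = 6 doses, or 600 mg/kg. After the Day 6 panel 3–8 doses remain, or 300–800 mg/kg. The longest stretch without scheduled chemistry is therefore 600–800 mg/kg. On the same basis (load as dose 1, panel at any time of day) it is 1,500–2,000 mg/kg under the current schedule.

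**The case against.** The best case for the plan is that children are not left unwatched after Day 2.

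- Table 3, note c expects routine daily blood draws.
- Section 7.5 has the site investigator review records routinely.
- Section 8.2.4 records clinically significant laboratory abnormalities as adverse events, and Section 5.1 summarizes adverse events and compares their occurrence by arm.
- Section 4.3.3 lets teams stop drug for adverse events, and Section 7.4 says children with known liver or kidney compromise are excluded.
- The manual of operations (Section 9) is not among the documents and may say more.

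The placement of the Day 2 panel is also sensible. The load, which is the new element, comes before it. The heaviest 24 hours (400 mg/kg) stay below the single 500 mg/kg dose that Section 2.6 describes as safe. Dosing after that is the earlier single-center RCT's regimen, and that trial found no liver or renal difference from placebo (Section 2.8). Section 2.6 reports no acidosis events in earlier arginine trials, and Section 2.8 reports no drug-related serious events in 83 children under the same IND.

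Most of this stands, and it limits the point to a modest one. It does not close the gap. Note c does not say which tests are run on the daily draws, and none of these provisions requires a chemistry test after Day 2 or 3. The earlier RCT's 5 days of 100 mg/kg three times a day come to 5 × 3 × 100 = 1,500 mg/kg, against up to 2,200 here. The load-plus-TID regimen was given to 4 children in the pharmacokinetic study (Section 2.7).

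A reader might go further in three ways that the documents do not support:

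- That bicarbonate has no repeat trigger. It has one, at 16; the problem is its width.
- That the regimen carries a known acidosis hazard. The unknown named in Section 2.6 concerns repeated higher doses, which the one-time load is meant to avoid.
- That the share of dose given after Day 2 is a share of risk. Nothing in the documents ties acidosis to cumulative mg/kg at this daily rate.

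**Conclusion.** The point holds as a low-cost safety improvement worth considering. The stop rules last as long as study drug is given, the last required panel is on Day 2 (Day 3 if flagged), no further repeat is required while a value stays flagged, and the bicarbonate trigger is one value wide. These follow from the current text without any assumption.

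The dose figures rest on 8-hour dosing with the load as dose 1. They describe a child who stays for all 21 doses; shorter stays have smaller shares. How many children stay beyond Day 2 or 3, and how often their clinicians order chemistry anyway, cannot be learned from the documents. Confidence is medium for that reason.

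**What to change.** 1. **Bicarbonate trigger.** Replace the single value 16 with a range above the stop limit, for example 16–18, for the sponsor's clinicians to confirm. State that the panel is repeated every 24 hours while any value stays flagged and study drug continues.
2. **Later chemistry.** For children still on study drug, add bicarbonate, creatinine and ALT to a routine clinical draw at a stated interval, for example Days 4 and 6, again for clinicians to confirm.

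Text to amend: Table 2 and its footnote, Table 3 and its note d, and the matching note in the Schema (Section 1.2).

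Cost: up to two added panels for a long stay, plus repeats for flagged values, and none on Days 4 or 6 for children already discharged. There is an assay cost, a small extra blood volume and an occasional added venipuncture when no clinical draw is made that day. The documents do not show how often that would happen.

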## 4.5 Data Collection

**Primary Outcome Measure:** *Time-to-crisis resolution*, defined as the time in hours from study drug delivery to time of last dose of parenteral opioid delivery.

- Data being collected: date and time of first study drug administration and last IV opioid treatment

### **Secondary Outcome Measures:**

- 1) Total parenteral opioid use (morphine equivalents, mg/kg)
  - Data being collected: time of IV placement, opioid monitoring
- 2) Pain scores at presentation vs. discharge; Daily highest and lowest pain scores recorded
  - Data being collected: Pain Scores (0–10 scale)
- 3) Three Patient Reported Outcomes (PROs),  performed within 12 hours of study drug delivery and on the day of discharge.
  - (a) PROMIS Pain Interference
  - (b) PROMIS Pain Behavior
  - (c) PROMIS Fatigue

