## Abstract

**Background:** Vaso-occlusive painful episodes (VOE) in sickle cell disease (SCD) are the leading cause of hospitalizations, emergency room (ED) visits, and missed school, and are associated with an increased mortality rate. There are no current therapies to relieve vaso-occlusion, with interventions limited to hydration and analgesia. Nitric oxide (NO), produced by the 5-electron oxidation of L-arginine, is a potent vasodilator and exerts pleiotropic effects on vascular and circulating blood cells, including the inhibition of platelet aggregation, down-regulation of adhesion molecules, and modulation of ischemia-reperfusion injury, all pathways adversely affected during VOE. In previous trials it has been found that pediatric SCD patients admitted with VOE have depleted plasma L-arginine levels. Additionally, a single-center randomized, double-blinded, placebo-controlled trial of arginine therapy in 54 children with VOE requiring hospitalization was completed. A reduction in total opioid use (mg/kg) by 54% and significantly lower pain scores at discharge in children who received 5 days IV L-arginine therapy every 8 hours compared to placebo, as well as a clinically relevant trend in reduced length of hospital stay of approximately 17 hours was observed. In pharmacokinetic studies, it was found that IV arginine induced a dose-dependent improvement in mitochondrial function in children with SCD hospitalized for pain.

**Design and Methods:** It is now proposed that these results are extended to a pivotal phase 3 trial of L-arginine for VOE. It is hypothesized that arginine is a safe intervention with opioid-sparing effects in pediatric patients with SCD and VOE that will decrease the time children experience severe pain. Aim 1 of this study will determine the efficacy of IV arginine therapy on the primary outcome, time-to-crisis resolution, as well as total parenteral opioid use (mg/kg) and pain scores in children with SCD and VOE compared to placebo (Efficacy). Aim 2 will monitor for safety of IV L-arginine (Safety). Aim 3 will characterize alterations in the arginine metabolome and mitochondrial function in children with SCD and VOE, and evaluate how it is impacted by IV arginine therapy (Exploratory).

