### 1.3 Hypotheses

The hypotheses of this study are:

1. Arginine therapy will decrease time-to-crisis resolution in children with an acute sickle cell vaso-occlusive pain episode compared to placebo.
2. Arginine therapy will lower total parenteral opioid use (mg/kg) compared to placebo.
3. Arginine therapy will improve pain scores compared to placebo.
4. Arginine will have a similar safety profile as placebo.
5. Arginine therapy will improve global arginine bioavailability and mitochondrial activity.

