## 2.2 Critical Barriers to Care for Patients with Sickle Cell Disease and Pain in the Emergency Department

*Acute care of patients with SCD and pain in the ED is a neglected area of sickle cell research.* Nationally, 78% of the nearly 200,000 annual ED visits for SCD are for a complaint of pain. Given the high ED utilization rate for pain in both adults and children with SCD, ED-based research has not received the amount of attention and funding that it deserves. Funding support for pain research that begins in the ED will help to remedy this disparity and potentially reduce the significant economic burden of this disease.

**Negative impact of opioids over time.** Emerging data supports long-term multi-organ side effects of opioids in SCD not appreciated years ago, and the recurrent/chronic use of large doses of opioids compounds the problem further. Opioid-induced endothelial-, mast cell-, renal mesangial-, and epithelial-cell-specific effects and proinflammatory signaling has been reported. Experimental and clinical studies suggest that opioids may exacerbate existent organ damage and also stimulate pathologies of their own. **Opioid-sparing pain therapies are needed; decreasing opioid use is a clinically important outcome of SCD-related morbidity.**

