## 2.8 Results of a single-center, double-blinded, RCT of arginine therapy for children with VOE

A total of 56 children  $> 3$  years old admitted to for VOE were enrolled in this NIH-supported arginine trial (*NHLBI K23 award HL-04386-05*). Mean age was  $13.9 \pm 4$  years (range 3.6–19 years), and 52% were female; 73% had Hb-SS, 18% Hb-SC and 9% carried S- $\beta$  thalassemia. Patients received IV arginine (100mg/kg TID) or placebo during hospitalization. **RESULTS:** Patient characteristics were similar between treatment and placebo groups. Mean time between ED triage and delivery of first randomized study drug dose was  $20.4 \pm 11$  hours, with no difference between the placebo and treatment arm. A significant reduction in opioid use (defined as total opioid use in morphine equivalents during hospitalization in mg/kg) by 54% was observed in the arginine treatment arm compared to placebo (mean  $\pm$  SEM:  $1.9 \pm 0.4$  mg/kg vs.  $4.1 \pm 0.8$  mg/kg;  $p=0.02$ ; Fig 4 A). Pain scores were similar at presentation, but significantly lower at discharge in the arginine arm vs. placebo (Fig 4 B). A clinically relevant trend of decreased hospital length of stay (LOS) by 17 hours favored patients treated with arginine. Total IV opioid use (mg/kg) correlated strongly to LOS ( $r=0.86$ ,  $p < 0.0001$ ), and represents a surrogate biomarker of LOS to evaluate study drug efficacy (Fig 4 C). Rates of ACS, transfusion and AEs were similar in both arms. No drug-related AEs were observed. No significant differences were observed between pre and post therapy liver or renal function, or hematological parameters in the arginine group vs. placebo.

[figure not shown]

Figure 4: Impact of arginine therapy on total opioid use, pain scores, & LOS. **A.** Arginine supplementation (unfilled circles) led to a significant & clinically relevant reduction in total opioid use by 54% over the course of the hospital stay compared to the placebo group (filled circles). The difference remains significant even when the 2 outliers with the largest total opioid use in the placebo arm are excluded from the analysis ( $p=0.04$ ). **B.** Pain scores were significantly lower at discharge in the arginine group compared to placebo by 2 cm. **C.** Correlation between Total Opioid Use (mg/kg) and Length of Hospital Stay (Days).

[figure not shown]

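### The opioid outcome counts parenteral doses only, so by itself it cannot support an opioid-sparing conclusion; add an in-hospital all-route total

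*Combined protocol and SAP*

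**What the plan says.** Secondary outcome 1 in section 4.5 is "Total parenteral opioid use (morphine equivalents, mg/kg"). Hypothesis 2 (sections 1.3 and 5) matches it: "Arginine therapy will lower total parenteral opioid use (mg/kg) compared to placebo". Section 5.1 analyses it like the primary outcome, by a stratified Van Elteren test, with Holm's adjustment across the secondary outcomes at 0.05 overall.

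The claim to be supported is broader. The Abstract hypothesises that "arginine is a safe intervention with opioid-sparing effects in pediatric patients with SCD and VOE", and section 2.2 states that "decreasing opioid use is a clinically important outcome of SCD-related morbidity", with no limit by route.

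On data capture, note h to Table 3 (section 4.5.1) covers parenteral opioids "including opioids delivered by the PCA device as well as any intravenous, intranasal and/or oral opioids used" and adds: "Data on daily opioid use will be collected and recorded". Nothing in section 4.5 or 5.1 adds the routes together. The nearest measure is the Medication Quantification Scale (MQS), a tertiary outcome.

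The primary outcome ends at the last parenteral opioid dose.

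**The concern.** Parenteral mg/kg falls when less opioid is given, and it also falls when the same opioid is given by mouth sooner. The outcome cannot tell these apart. The primary endpoint cannot either, because an earlier change of route also brings forward the last parenteral dose. If arginine shortens the parenteral phase and oral opioid fills the gap, both results favour arginine while total exposure is unchanged. The argument in section 2.2 is about exposure.

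At stake is the wording of a main conclusion. Lower parenteral use would be a true finding. Opioid-sparing would not follow from it.

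The text is also unclear in two places. Note h places oral and intranasal doses under a heading about parenteral opioids, so the routes that enter the outcome are not certain. The previous single-center trial's 54% reduction is called total opioid use in the Abstract and section 2.8, but parenteral use in section 2.1.

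**Working it through.** **1. The plan's own figure.** Section 2.8 gives means (SEM) of 1.9 (0.4) and 4.1 (0.8) mg/kg.
- Reduction: (4.1 − 1.9)/4.1 = 53.7%, which reproduces 54%.
- Welch t = 2.2/√(0.4² + 0.8²) = 2.46. With 27 or 28 per arm (assumed), p = 0.018 to 0.019, which agrees with the stated 0.02.

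**2. What substitution does.** Suppose a share f of a 2.2 mg/kg parenteral difference is replaced by equivalent oral opioid (f is assumed; the documents give no oral doses). The parenteral reduction stays at 54% throughout.

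| f | All-route reduction, as % of 4.1 mg/kg |
|---|---|
| 0 | 54% |
| 0.25 | 40% |
| 0.5 | 27% |
| 0.75 | 13% |
| 1 | 0% |

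**3. Size of a pure route switch.** From the documents: 0.7 days (section 5.2), 4.1 mg/kg and the SEMs (section 2.8), and 180 per arm. Assumed: 4.1 mg/kg spans 3 to 4 days, there were 27 per pilot arm, and oral replacement is complete.
- Dose rate: 4.1/4 to 4.1/3 = 1.03 to 1.37 mg/kg/day.
- Fall at the average rate: × 0.7 = 0.72 to 0.96 mg/kg, or 17.5% to 23% of 4.1.
- Fall if the end-of-crisis rate is half the average: 0.36 to 0.48 mg/kg.
- SDs: 0.8√27 = 4.16 and 0.4√27 = 2.08.
- SE at 180 per arm: √((4.16² + 2.08²)/180) = 0.35.

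| End-of-crisis rate | z | Significant at 0.05 | Significant at 0.01 |
|---|---|---|---|
| Average | 2.07–2.76 | 54–79% | 31–57% |
| Half | 1.04–1.38 | 18–28% | 6–12% |

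The last two columns are Φ(z − 1.96) and Φ(z − 2.576). The 0.01 column is Holm's first step if there are five secondary tests (opioid, pain and three PROs; the count is an assumption). With the placebo SD in both arms, the average-rate row at 0.05 becomes 37–59%.

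**4. Rank-test illustration.** The table above is a normal approximation, not the planned test. As a separate check, 4,000 trials per setting were simulated with 166 per arm and an unstratified Wilcoxon test at 0.05. Assumed: lognormal duration with mean 2.5 to 3.0 days and SD 2.13; dose rate 1.4 mg/kg/day with SD 0.7; every switched dose replaced by mouth.
- A 0.35-day earlier switch made the parenteral test significant in 47–63% of trials.
- A 0.7-day switch did so in 97–99.7%.
- The all-route test stayed at 4–6%, as it must when no opioid is saved.

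The answer therefore depends heavily on the assumed distributions. None of these figures is a forecast.

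**The case against.** The strongest reply is that outcome and hypothesis agree. Hypothesis 2 says parenteral both times it appears, and the Synopsis and Specific Aim 1 use the same term. The opioid-sparing phrase stands in the Abstract, and section 2.2 is background. This is correct: the parenteral test answers its own hypothesis, and what remains is the broader wording.

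Three stronger readings are tempting, and the documents do not support them.
- **A false-positive mechanism.** The trial is double-blind. Without a drug effect, neither arm is expected to switch earlier. The percentages above assume a true shortening of the parenteral phase, so they say nothing about type I error.
- **A pilot that counted all routes.** Section 2.8 describes its outcome as "defined as total opioid use in morphine equivalents during hospitalization in mg/kg", but it also reports total IV opioid use, and section 2.1 calls the same 54% parenteral. The documents do not settle which it was.
- **A repeat of the primary endpoint.** The r = 0.86 in section 2.8 relates IV opioid to length of stay in the pilot. Section 5.2 says only that length of stay parallels crisis resolution.

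The MQS answers the concern in part. It is scored daily and is not described as parenteral only. But it is tertiary, its scoring is not given, and it is a medication scale, not an opioid dose in mg/kg.

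The size may also be modest. On the average-rate assumption, a full-replacement switch accounts for 0.72/2.2 to 0.96/2.2, or 33% to 44%, of the pilot difference.

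An all-route total has a limit of its own. Section 5.1 expects length of stay to follow the primary result, so arginine children may take oral opioid at home sooner. Table 3 marks opioid monitoring in the Day 14/28 column, but its notes describe only nursing-shift records and, after discharge, ED revisits and admissions.

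**Conclusion.** The point holds as a limit on interpretation. Lower parenteral use is a legitimate result under that name, but it does not by itself show that opioid was spared. An earlier route switch moves the outcome in arginine's favour with nothing saved.

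The size is unknown because no oral doses are given. Under full replacement and a 0.7-day earlier switch, the fall is about 0.36 to 0.96 mg/kg. It is significant in roughly 18–79% of trials at an unadjusted 0.05 by normal approximation, and in fewer at Holm's stricter steps. Those figures rest on the assumed 3 to 4 day span, end-of-crisis dose rate and pilot arm size. The rank-test illustration gave higher values under different assumptions. Partial replacement would leave some true saving.

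The primary analysis, type I error and sample size are unaffected. The change is worth making because the in-hospital data are already recorded and it alters what the trial may conclude.

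**What to change.** In sections 4.5 and 5.1:
- Keep total parenteral opioid as secondary outcome 1.
- Add a supportive outcome, outside the Holm family: total opioid by all recorded routes (parenteral, intranasal, oral), in mg/kg morphine equivalents, using a prespecified conversion table.
- Run its window from first study drug to hospital discharge. It must not end at the last parenteral dose, or the switched oral doses drop out. State the window for the parenteral total as well, since section 4.5 gives none.
- Use the same stratified Van Elteren test, and report the oral component by arm.
- Label it in-hospital opioid use. State that home doses are not clearly captured, so earlier discharge can still lower it.
- Use the opioid-sparing wording only if the all-route result agrees in direction. Otherwise report reduced parenteral use.

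In note h, state which routes enter the parenteral outcome. Reconcile the total (Abstract, section 2.8) and parenteral (section 2.1) descriptions of the 54%.

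Cost: SAP wording, a conversion table and one further analysis of recorded data. The downside is some added variance from conversion factors and a stricter condition for the wording.
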